### **6.1.4. Handling of Multiple Observations**

Priority will be given to scheduled visits. Unscheduled assessments will be used if there are no scheduled visit assessments in the visit window per SOE; visit window in general is  $\pm 1$  day, unless specified otherwise; follow-up visit is  $\pm 2$  days.

### **6.1.5. Handling of Missing or Partial Dates**

Date imputation will only be used for computational purposes; e.g., treatment-emergent status or identifying concomitant medications. Actual data values as they appear in the clinical database will be shown in the subject data listings.

#### **6.1.5.1. Adverse Event Date Imputations**

In cases of incomplete dates for adverse events (AEs), the missing component(s) will be assumed as the most conservative value(s) to conservatively capture AEs with missing start dates as treatment-emergent AEs (TEAEs) unless TEAE status was disqualified based on a pre-treatment stop date/time. The imputation rules are as follows:

- If “day” is the only missing field, impute the “day” as the first randomized dose date if the month and year of randomization are equal to the AE start month and year; otherwise, impute the “day” as the first day of the AE start month.
- If “day” and “month” are missing, impute the “day” and “month” as the day and month of the first randomized dose date if “year” is the same as the year of randomization; otherwise, impute January 1 of the non-missing year.
- Missing time will not be imputed. If “time” is missing and the start date is the same as the first dose date, then the time is assumed to be after the first dose time so that the event will be classified as treatment emergent.
- If the start date is completely missing:
  - and from the end date (either complete or partial date) it cannot be deduced to be prior to the first dose date, then the AE will be assigned as a TEAE.
  - and from the end date (either complete or partial date) it can be deduced to be prior to the first dose date, then the AE will not be assigned as a TEAE.

#### **6.1.5.2. Medication Date Imputations**

Imputation of partial medication end dates is done for the purpose of classifying concomitant status of medications. The imputation rules are as follows:

For medications with partial end dates:

- If “day” is the only missing field, impute the “day” as the last day of the month.
- If “day” and “month” are the missing fields, impute the “month” and “day” to Dec 31.
- If end date is completely missing, then medication will be classified as a concomitant medication.

#### **6.1.6. Handling of Missing Efficacy Data**

Missing efficacy data will not be imputed.

### **6.2. Subject Disposition**

Subject disposition will be presented for all subjects in the randomized analysis set. The count and percentage of subjects who are randomized, who are treated, who completed or discontinued from the study will be summarized by treatment group and overall. Furthermore, subjects who discontinued from the study will be summarized by reason for early discontinuation such as:

- Adverse event (or serious adverse event)
- Protocol Violation
- Lost to follow-up
- Voluntary withdrawal of consent
- Discretion of Investigator
- Pregnant or breast feeding
- Study discontinuation by Sponsor

- Other

### **6.3. Demographics and Baseline Characteristics**

Demographic and baseline characteristics such as, but not limited to, age, sex, race, ethnicity, height, weight, body mass index, waist circumference, MRI-PDFF, HbA1c and FPG will be summarized descriptively for all subjects overall and by treatment in the randomized analysis set. If composition of the Safety analysis set is different from that of the randomized population, demographics and baseline characteristics will be also summarized in the safety analysis set.

### **6.4. Medical History**

Medical history will be summarized descriptively, with count and percentage, by coded term (using MedDRA version 22.0) and treatment group for the Safety analysis set.

### **6.5. Subject Eligibility**

Subject eligibility data will only be listed.

### **6.6. Study Drug Administration**

Subjects will receive their assigned dose orally with 240 mL of water. The total drug exposure (mg), the duration of exposure (days), drug dose modification, and the drug compliance will be summarized by treatment.

The duration of exposure is defined as (date of last dose – date of first dose + 1 + 7). The drug compliance is defined as number of capsules taken/ {(date of last dose – date of first dose + 1 + 7)\*2/3}\*100. For each treatment group, drug compliance will be summarized by compliance category (<80%, 80-120%, and >120%).

### **6.7. Prior and Concomitant Medication**

Concomitant medication is defined as any medication given in addition to the investigational product (including over-the counter medications, herbal medications, and vitamin supplements) administered between screening and follow-up.

The latest version of the World Health Organization (WHO) Drug Global dictionary (Global B3 Mar 2019) will be used to categorize verbatim descriptions of non-study medications into the Anatomic Therapeutic Chemistry (ATC) classification system. Each verbatim name will be classified by anatomical main group (ATC level 1), therapeutic subgroup (ATC level 2), pharmacological subgroup (ATC level 3), chemical subgroup (ATC level 4), and trade name.

The number and percentage of subjects receiving any concomitant medications will be summarized by treatment group and ATC classification (ATC level 2 and level 4) for the Safety analysis set.

## 6.8. Protocol Deviations

Protocol deviations will be summarized by the category of important or non-important by treatment group for the Safety analysis set. Important protocol deviations are thought to have possible impacts on the analysis.

## 6.9. Analysis of Pharmacokinetics Endpoints

### 6.9.1. Plasma Concentration of FT-4101

PK concentrations will be summarized descriptively by treatment group, visit and nominal time point in the PK analysis set, including the arithmetic CV%. Concentrations that are below the limit of quantitation (BLQ) will be treated as zero for the computation of descriptive statistics.

Individual subject concentration-time data will be graphically presented on linear and semi-logarithmic scales with a separate graph for each dose level. Figures of arithmetic mean concentration-time data ( $\pm$ SD, as appropriate) will be presented for each treatment on linear and semi-logarithmic scales. Plots will be presented for PK samples collected during the first and last cycle and for all trough samples collected cumulatively across all cycles.

A subject's data listing of PK concentration will be provided. Subject's PK concentrations which are not included in PK parameter derivation will be flagged. Time difference between nominal time point and actual sampling time point will be presented.

### 6.9.2. Pharmacokinetic Parameters of FT-4101

For PK parameter calculations, BLQ concentrations will be assigned a value of zero if they precede quantifiable samples in the initial portion of the profile and will otherwise be treated as missing. Missing PK concentration data will not be imputed.

PK parameters will be estimated separately from single dose profiles (C1D1) and multiple dose profiles (C4D14/15). The following are the PK parameters that will be estimated for FT-4101 in plasma by non-compartmental methods using actual elapsed time from dosing:

- Maximum concentration ( $C_{\max}$  [ng/mL])
- Dose-normalized  $C_{\max}$  ( $C_{\max}/D$  [mL $^{-1}$ ])
- Time to maximum concentration ( $T_{\max}$  [h])
- Area under the concentration-time curve for a dosing interval, calculated by linear up/log down trapezoidal summation ( $AUC_{\tau}$  [h\*ng/mL])
- Area under the concentration-time curve in the sampled matrix from zero (predose) to time of last quantifiable concentration, calculated by linear up/log down trapezoidal summation ( $AUC_{0-\text{last}}$  [h\*ng/mL])
- Area under the concentration-time curve in the sampled matrix from zero (predose) extrapolated to infinite time, calculated by linear up/log down trapezoidal summation ( $AUC_{0-\infty}$  [h\*ng/mL])
- Dose-normalized  $AUC_{0-\text{last}}$  [h/mL]
- Dose-normalized  $AUC_{\tau}$  [h/mL]

- Trough plasma concentrations ( $C_{trough}$  [ng/mL]) at steady state (C1D15 and all 24h post-dose time points thereafter)
- Apparent terminal half-life ( $t_{1/2}$  [h])
- Apparent systemic clearance after extravascular dosing (CL/F [L/h])
- Apparent volume of distribution following extravascular dosing ( $V_z/F$  [L])

Half-life dependent parameters ( $AUC_{0-\infty}$ , CL/F,  $V_z/F$ ) will only be presented if the data indicate that the sample collection period is adequate to determine  $t_{1/2}$ .

PK parameters will be summarized descriptively by visit and treatment group in the PK analysis set.

## **6.10. Analysis of Preliminary Efficacy and Pharmacodynamic Endpoints**

Analysis of preliminary efficacy and PD endpoints will use the planned treatment assignment. Placebo subjects will be pooled for analysis. The percent change will be considered primary over absolute change.

### **6.10.1. Analysis of Primary Preliminary Efficacy Endpoint**

The primary preliminary efficacy endpoint is:

- Reduction (absolute and relative) of % liver fat on MRI-PDFF at 12 weeks

#### **6.10.1.1. Reduction of Liver Fat Assessed by MRI-PDFF at 12 Weeks**

The observed values and the change from baseline and the percent change from baseline of liver fat estimated from MRI-PDFF will be summarized descriptively by visit and treatment group.

The change and percent change at Week 12 in liver fat (%) as assessed by MRI-PDFF will be analyzed by a Wilcoxon-Mann-Whitney test. The test will be one-sided and use a significance level of 0.05. Subjects in each dose group will be tested against the pooled placebo subjects from each cohort.

Multiplicity adjustment to control the alpha level will be accomplished using Holm's Sequential Bonferroni procedure as previously described.

If change or percent change of MRI-PDFF is not obvious deviated from symmetric distribution, a two-sample independent t-test will be carried out to compare liver fat (%) between FT-4101 treatment and the pooled placebo as supportive analysis, based on one-sided significance level of 0.05. P value will be corrected using Holm's Sequential Bonferroni procedure as previously described.

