#### 12.5.1.1 Liver Fat Assessed by MRI-PDFF at 12 weeks

The observed values and the change (absolute) from baseline and the percent change from baseline of liver fat estimated from MRI-PDFF will be analyzed descriptively by treatment group and visit.

Change at Week 12 (absolute and relative) in percentage of liver fat as assessed by MRI-PDFF will be analyzed by a Wilcoxon rank-sum test. The test will be one-sided and use a significance level of 0.05. Subjects in each dose group will be tested against the pooled placebo subjects from each cohort.

If more than one dose of FT-4101 is evaluated, control of the alpha level will be accomplished using Holm's Sequential Bonferroni procedure [Holm 1979] to test each FT-4101 dose against the pooled placebo subjects.

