### **3.4. Sample Size Consideration**

With 10 evaluable subjects in the treated group and 10 evaluable subjects in the control group, there is 84% power to detect a difference of 20% in MRI-PDFF between any dose of FT-4101 treated group and the pooled placebo subjects in cohorts A and B, assuming a standard deviation of 14% using a one-sided Wilcoxon-Mann-Whitney test with an alpha of 0.05.

The total sample size will be 30 subjects, 15 subjects per cohort randomized 2:1 to receive FT-4101 or placebo.

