### **6.1.2. Hypothesis Testing and Multiplicity Adjustment**

The primary preliminary efficacy endpoint will be tested using a one-sided test at an alpha level of 0.05. The null hypothesis and alternative hypothesis are presented below.

$$H_0: \text{Diff} \geq 0$$

$$H_a: \text{Diff} < 0$$

Where Diff is the mean difference: FT-4101 minus Placebo.

If more than one dose of FT-4101 is evaluated, control of the alpha level will be accomplished using Holm's Sequential Bonferroni procedure to test each FT-4101 dose against the pooled placebo subjects. There will be two comparisons.

The p-values of the multiple comparisons will be ordered from smallest to largest. The corrected p-value from each comparison, starting from the smallest original p-value, will be calculated based on the following formula:

$$p_{\text{Bonferroni},i|C} = (C - i + 1) * p$$

where the number of comparisons is  $C$ , index  $i$ , ranges from 1 to  $C$ , and the original p-value that is to be corrected,  $p$ . Corrected p-values less than 0.05 will be considered statistically significant.

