#### **6.10.2.1. Reduction of Liver Fat Assessed by MRI-PDFF at 6 Weeks**

The reduction of liver fat assessed by MRI-PDFF at 6 Weeks will be analyzed similar to the primary preliminary efficacy endpoint.

A supportive analysis using a mixed effects model with repeated measures (MMRM) will be used to analyze the change from baseline, both absolute change and percent change (absolute and relative), to week 6 and week 12; the model will include change in liver fat (%) on MRI-PDFF (absolute and relative) as dependent variable, treatment group as independent variable, covariates including baseline liver fat (%), visit, interaction term of treatment and visit, and a random slope and intercept per subject. Model parameters will be estimated using the restricted maximum likelihood method (REML). An unstructured covariance matrix will be used to estimate the intercept-slope covariance. In case of convergence problem, other covariance structure will be used in the order of compound symmetry and variance component. The least squares (LS) means and their corresponding 90% confidence intervals and p-values at one sided test will be presented. The LS mean difference between treatment groups will be presented along with the 90% confidence interval and p-value.

The following SAS code will be used for the MMRM analysis:

```
Proc mixed method=reml;
  Class usubjid visit treat;
  Model change [or percentchange] = baseline visit treat
  treat*visit /ddf=kr solution alpha=0.05;
  repeated visit /subject=usubjid type=un;
Run;
```

Where treat=treatment group (pooled placebo, FT4101 3.0 mg, FT 4101 4.5 mg), baseline = baseline liver fat (%), change = absolute change in liver fat (%) from baseline, percentchange = relative percent change in liver fat (%) from baseline, visit=study visit (Week 6, Week 12), usubjid = subject ID.

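### The deciding Week 12 test leaves the remaining association between baseline liver fat and change uncorrected; a rank ANCOVA would protect it against baseline imbalance at little cost

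*SAP*

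**What the plan says.** SAP 6.10.1.1 states that Week 12 change and percent change in liver fat "will be analyzed by a Wilcoxon-Mann-Whitney test". Protocol 12.5.1.1 names the same test: the outcome "will be analyzed by a Wilcoxon rank-sum test". SAP 6.10.1.1 adds: "The test will be one-sided and use a significance level of 0.05". Each dose is compared with the placebo subjects of both cohorts combined. SAP 6.1.2 applies Holm's procedure and notes: "There will be two comparisons". SAP 6.10 ranks percent change above absolute change.

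No covariate or stratum enters this test, and the supportive t-test in SAP 6.10.1.1 is also unadjusted. Baseline liver fat is nevertheless known for everyone analysed. It is an entry criterion (Protocol 7.1), the screening scan is centrally read as the baseline value (Protocol 9.1.17.6), and the efficacy set requires it (SAP 4.4). The supportive repeated-measures model for Weeks 6 and 12 does use it, with "covariates including baseline liver fat (%), visit, interaction term of treatment and visit" (SAP 6.10.2.1). Protocol 8.7 describes 2:1 randomization and no stratification by liver fat.

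**The concern.** Taking change or percent change refers each subject to their own baseline. It does not remove a remaining link between baseline and change, such as regression to the mean. If that link exists, a group that starts higher will tend to show a larger fall without any drug effect, and the deciding test has no correction for it.

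Imbalance can arise in two ways. With 10 subjects a side, chance differences in baseline are sizeable. In addition, five of the ten controls for each dose were randomized in the other cohort, and Cohort B opens only after at least 12 Cohort A subjects have completed two cycles (Protocol 6.4). Randomization does not balance a dose group against that half of its controls. At stake are the error rate and power of the primary contrast in a trial that happens to be imbalanced.

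**Working it through.** **Inputs from the documents.** SAP 3.4 works with 10 v 10 evaluable subjects and a target difference of 20, "assuming a standard deviation of 14% using a one-sided Wilcoxon-Mann-Whitney test with an alpha of 0.05". Its stated power is 84%. With two comparisons, the first Holm step is at 0.05/2 = 0.025 one-sided. The correlation r between baseline and change within arm is not given, so every result below is shown over assumed values.

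**1. The plan's power figure.** Noether's formula, with P the chance that an active subject has the lower value:
- P = Φ(20/(14√2)) = Φ(1.010) = 0.844
- Power = Φ(√(12 × 20 × 0.25) × (0.844 − 0.5) − 1.645) = 84.6%

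This agrees with the stated 84%. It applies at one-sided 0.05, before Holm. By simulation with normal data, the exact Wilcoxon test has 89.9% power at 0.05 and 81.8% at 0.025 (Noether at 0.025: 75.9%).

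**2. How often baseline is imbalanced by chance.** The standard error of a difference in means is √(1/10 + 1/10) = 0.447 SD. The chance of a difference of at least 0.5 SD in either direction is 2 × (1 − Φ(0.5/0.447)) = 2 × (1 − Φ(1.118)) ≈ 26%.

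**3. What imbalance does.** Simulated at 10 v 10 with difference 20 and SD 14. Each cell is unadjusted Wilcoxon / rank ANCOVA on baseline.

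| Situation | r = -0.3 | r = -0.5 | r = -0.7 |
|---|---|---|---|
| False positives at 0.05, active arm at least 0.5 SD higher at baseline | 9.6% / 4.9% | 14.9% / 5.3% | 21.9% / 6.1% |
| Power at 0.025, active arm at least 0.5 SD lower at baseline | 69% / 75% | 57% / 81% | 43% / 91% |
| False positives at 0.05, dose's own cohort 0.5 SD higher at baseline, five controls from the other cohort | 6.2% / 5.1% | 7.4% / 5.2% | 8.9% / 5.2% |

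The 0.5 SD cohort shift is an assumption. Over all trials with exchangeable cohorts, the exact Wilcoxon rejects a true null in about 4.5% of trials at nominal 5%.

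**4. Overall power at the first Holm step (one-sided 0.025).** The rank ANCOVA is Quade's: rank both variables over the 20 subjects, regress the ranks of change on the ranks of baseline, and compare the residuals by t on 10 + 10 − 2 = 18 df.

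| Absolute value of r | Wilcoxon | Rank ANCOVA | Difference (points) |
|---|---|---|---|
| 0 | 81.7% | 81.2% | -0.5 |
| 0.3 | 81.4% | 83.6% | +2.2 |
| 0.5 | 81.6% | 89.0% | +7.4 |
| 0.7 | 81.4% | 95.9% | +14.5 |

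Rank ANCOVA rejects a true null in 2.5–2.6% of trials.

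**5. Which r is plausible on the percent-change scale.** Two simple models, both assumed:
- *Drug effect proportional to baseline.* Percent change is then unrelated to baseline, so r ≈ 0. With baseline mean 18 and SD 6, cut at the 10% entry limit, Wilcoxon has 81.7% and rank ANCOVA 80.9%: a loss of 0.8 point.
- *Stable liver fat with measurement noise (regression to the mean), SD of percent change 14%.* Approximately r = −0.14/(2 × CV), where CV is the baseline coefficient of variation. A CV of 20% gives −0.35 and 50% gives −0.14 (simulated: −0.34 and −0.12). The rank ANCOVA gain at 0.025 runs from 0.4 point (CV 50%: 82.1% to 82.5%) to 3.8 points (CV 20%: 81.6% to 85.4%).

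For |r| of 0 to 0.3 the effect on power is therefore about -1 to +3 points.

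**The case against.** A reader might infer that the primary test ignores baseline, is invalid, or gives up a good deal of power. None of these is supported.

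- **Ignoring baseline.** Both tested outcomes are changes from baseline, and percent change takes priority. Only the remaining association is uncorrected.
- **Validity.** Under randomization with exchangeable cohorts the Wilcoxon keeps its overall error rate. The inflated figures are conditional on an imbalance, or on an assumed cohort shift, and on an assumed r.
- **Power.** Powers of 89–96% need |r| of 0.5–0.7 in both arms, which no document supplies. A correlation near -0.4 can be derived, but for absolute change in the treated arm only. With a proportional 20% fall, baseline mean 18 and SD 6, it is −(0.2 × 6)/√((0.2 × 6)² + 0.14² × (18² + 6²)) = −1.2/2.92 = −0.41. On the primary percent-change scale the same model gives r near 0.
- **Pooled placebo.** Both cohorts share one set of entry criteria, so no systematic difference in baseline fat is shown. A cohort difference acting through anything else would not be removed by adjusting for baseline PDFF.

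It is also fair that the sample size was computed for the test that will be used, that Protocol 6.3 calls the study exploratory, that baseline PDFF will be tabulated by treatment (SAP 6.3), and that a baseline-adjusted Week 12 estimate is already planned. These points lower the priority but do not remove the point. The adjusted model is only supportive, and its text (random slope and intercept) does not match its code (a REPEATED statement only). If it and the Wilcoxon disagree, the Wilcoxon decides.

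**Conclusion.** The point stands as a cheap improvement, not as the correction of an error. The test that decides the primary efficacy question does not correct for the remaining association between baseline PDFF and change, although the data are there and the SAP already treats baseline as a useful covariate.

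The main benefit is protection against imbalance, whether by chance or between sequential cohorts. At an assumed r of -0.3, false positives in a trial with the active arm at least 0.5 SD higher fall from about 10% to about 5%. With a 0.5 SD cohort shift they fall from 6.2% to 5.1%. The benefit shrinks as r approaches 0. The power case alone is weak on the primary scale and becomes material only if |r| is 0.5 or more. The sizes rest on normal data, 10 evaluable subjects a side, the plan's difference and SD, and assumed correlations. Adjustment deals only with cohort differences that act through baseline PDFF.

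**What to change.** In SAP 6.10.1.1, make the primary test a one-sided rank ANCOVA (Quade) of Week 12 percent change on baseline PDFF, for each dose against pooled placebo. Keep the Holm procedure and the one-sided 0.05 level. Keep the unadjusted Wilcoxon as a sensitivity analysis, and use the same method at Week 6. Record the change from Protocol 12.5.1.1 in SAP section 7 before unblinding.

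A rank method is preferable to ordinary ANCOVA here. With heavy-tailed (Laplace) errors at one-sided 0.05 and r = 0, ordinary ANCOVA falls to 89.8% against 93.0% for Wilcoxon, while rank ANCOVA has 92.7%.

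The cost is SAP wording and a few lines of code, with no new data. The downside is under 1 point of power if baseline is unrelated to percent change.

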## **6.10.2. Analysis of Secondary Preliminary Efficacy and Pharmacodynamic Endpoints**

The secondary preliminary efficacy endpoints are:

- Reduction (absolute and relative) of % liver fat on MRI-PDFF at 6 weeks
- Proportion of subjects experiencing a relative reduction of 30% or greater of liver fat at week 12 as assessed by MRI-PDFF

The secondary PD endpoints are:

- Reduction of liver biochemistry markers: Alanine aminotransferase (ALT), Aspartate aminotransferase (AST), Gamma-glutamyl transferase ( $\gamma$ GT), Alkaline phosphatase, and Total bilirubin

